## 2.3 Randomization and Blinding

### 2.3.1 Method of Randomization

Participants are randomized on Day 1 following confirmation of eligibility and immediately prior to IP administration. Study personnel randomize the participant within the electronic data capture (EDC) system, and a randomization number is generated from the EDC randomization module. The EDC randomization module matches the randomization number to an IP kit available at the site and informs the study personnel of the assigned kit. Study personnel use the appropriate kit for administration to the participant.

Participants are considered enrolled once a randomization number has been assigned within the EDC system. The study is conducted as a double-blind study through Day 183 EOS. The participants, site personnel (including the investigator) and the Sponsor do not know participants' individual treatment assignments until all participants have completed their participation in the study through the Day 183 EOS and the database has been cleaned and locked.

### 2.3.2 Randomization Errors

A *misrandomization* is defined as a participant receiving a study treatment other than the one assigned by randomization.

A *stratification error* occurs when a participant is randomized based on incorrect stratification information at Day 1 (baseline) or if a participant is mistakenly put into a wrong block.

In either case, the participant uses up one position in the assigned block and randomization continues. Both misrandomization and stratification errors are reported as protocol deviations.

### 2.3.3 Blinding and Unblinding

Study participants, the investigator, and study site personnel remain blinded to all randomization assignments throughout the study. Sponsor's Medical Monitor and personnel who are in regular contact with the study site and/or involved with documentation associated with the study remain blinded to all participant randomization assignments.

Only the unblinded third-party vendor is unblinded to produce preliminary safety and immunogenicity analyses through the Day 29 Visit for all participants. Results are reported to the Sponsor only at the treatment group summary level, preserving the double-blind status on the participant level for the duration of the study.

The following safeguards are employed to reduce the risk of inadvertent unblinding:

- Use of a standardized pre-filled syringe and injection volume for all injections.
- All PXVX0317 and placebo syringes have a semi-transparent barrel cover to mask any difference in appearance between placebo and PXVX0317.

- No Sponsor personnel has access to the randomization schedule. No site personnel have access to treatment assignments. The Randomization and Trial Supply Management component of the vendor EDC system allows for unblinding of individual participants in an emergency by the investigator. The investigator must attempt to notify the Sponsor's Medical Monitor prior to unblinding and must notify the Medical Monitor within 24 hours after unblinding at the latest. If the investigator is unable to access the vendor EDC system, then the Medical Monitor may assist by calling the vendor EDC helpline for emergency unblinding. Emergency unblinding is documented as a protocol deviation.
- Assays are run in a blinded manner. The assay titer results are not delivered to the Sponsor data management and analysis team until after database lock, as they are potentially unblinding. However, unblinded assay titer results are delivered to the third-party vendor for all participants through the Day 29 Visit for preliminary safety and immunogenicity analyses.
- Should any participant or site personnel become inadvertently unblinded, the investigator promptly (within 24 hours of their awareness of the error) discloses the event to the Sponsor's Medical Monitor in a blinded fashion (disclosing only participant number, not treatment) so that corrective action can be initiated. The unblinding sequence of events is documented and retained as source documents. A protocol deviation is entered in the electronic case report form (eCRF).

Refer to the separate Blind Maintenance Plan for further details.

As noted above, the third-party vendor responsible for preliminary safety and immunogenicity analyses receives both unblinded participant randomization assignments and unblinded assay titer results for all participants through the Day 29 Visit. This vendor is independent from the Sponsor and is instructed to maintain the Sponsor's blind. The Sponsor, participants, and site personnel are not unblinded at the participant level until all follow-up visits are completed for the study through Day 183 EOS.

An individual participant is considered to have completed study participation after completion of the Day 183 EOS and any required safety follow-up. Upon completion of the study for all participants, the study database is cleaned and locked per the Sponsor's standard operating procedures. Unblinding occurs per the Sponsor's standard operating procedures after the SAP is finalized and approved and the database is locked. The Sponsor completes an unblinding request form, approved by the study statistician and medical/scientific reviewer and sends the completed and approved form to the EDC vendor to request release of the randomization assignments to the Sponsor for final analysis.

### **3 STUDY ENDPOINTS**

#### **3.1 Immunogenicity Endpoints**

##### **3.1.1 Coprimary Immunogenicity Endpoints**

- Difference in anti-CHIKV SNA seroresponse rate (PXVX0317 minus placebo) and associated 95% confidence interval (CI) at Day 22.

**Note:** Seroresponse rate (considered the presumptive seroprotection rate) is defined as the percentage of participants who achieve an anti-CHIK SNA titer █.

- Anti-CHIKV SNA GMT and associated 95% CIs at Day 22 for PXVX0317 and placebo.

Each endpoint is summarized for both age strata pooled and for individual age strata, as well as by sex and by race group (white and non-white) and ethnicity group (Hispanic or Latino and Not Hispanic or Latino).

### 3.1.2 Secondary Immunogenicity Endpoints

- **Key Secondary Immunogenicity Endpoints:** Difference in anti-CHIKV SNA seroresponse rate (PXVX0317 minus placebo) with associated 95% CI at Day 15 and Day 183, in that order.
- Anti-CHIKV SNA GMTs by study arm with associated 95% CIs at Day 15 and Day 183.
- Geometric mean fold increase (GMFI) in anti-CHIKV SNA titer from baseline (Day 1) to Days 15, 22 and 183.
- Number and percentage of participants with an anti-CHIKV SNA titer  $\geq 15$  and 4-fold rise over baseline at Days 15, 22 and 183.

Each endpoint is summarized for both age strata pooled and for individual age strata.

### 3.1.3 Exploratory Immunogenicity Endpoint

- Geometric mean titers and associated two-sided 95% CIs for neutralizing antibodies against various CHIKV genotypes measured at Day 22 (and at baseline if necessary) for a subset of participants in the PXVX0317 group.

## 3.2 Safety Endpoints

- Incidence of solicited AEs through Day 8 for PXVX0317 and placebo.
- Incidence of unsolicited AEs through Day 29 for PXVX0317 and placebo.
- Incidence of AESI and SAEs and MAAEs through Day 183 for PXVX0317 and placebo.

## 3.3 Pharmacokinetic Endpoints

Not applicable.

## 3.4 Pharmacodynamics Endpoints

Not applicable.

## 3.5 Exploratory Endpoint

See Section 3.1.3.

## 4 POWER AND SAMPLE SIZE CONSIDERATIONS

### 4.1 Sample Size and Power for Immunogenicity

Based on the data from the Phase 2 study (protocol PXVX-CV-317-001), the seroresponse rate for PXVX0317 vaccine is expected to be approximately █ versus <5% for the placebo participants. With an assumed 10% rate of non-evaluable participants, the power to show superiority over placebo with 180 PXVX0317 vaccine and 180 placebo evaluable participants is >99.9% for the combined age groups.

The difference in seroresponse rate between PXVX0317 and placebo groups that is considered clinically relevant is █. With 180 baseline seronegative PXVX0317-treated participants and a target seroresponse rate of █ vs. a rate of 5% for placebo, the width of a two-sided 95% CI would be  $\pm 5.4\%$ . If the target PXVX0317 seroresponse is █, the width would be  $\pm 6.9\%$ . Therefore, the difference in seroresponse rates must be above █ for the lower bound of the 95% CI for the difference to be █.

## 5 DATA CONSIDERATIONS

### 5.1 Participant Screening

#### 5.1.1 Screen Failure Participants

A note to file was generated for this study to document that no data collection conventions were prespecified for screen failure participants. The only data domains considered necessary for screen failure participants are demographics, eligibility criteria, and disposition data.

#### 5.1.2 Rescreening and Empty Participant Identifiers

The study protocol states that rescreened participants should use the original participant identifier. However, in some cases, sites rescreened participants with a new participant identifier number. Once data were consolidated for rescreened participants into the participant identifier used for randomization, an empty participant identifier resulted. In other cases, extra participant identifier numbers were generated inadvertently. These blank identifiers were not deleted from the study database for technical reasons. A note to file was written for this study to specify that participant identifiers empty of data (i.e., blank participant IDs) would not be mapped to SDTM nor included in any clinical study report analyses.

### 5.2 Protocol Deviations

A deviation occurs when site personnel or a participant does not adhere to the protocol's stipulated requirements, whether inadvertently or planned. All identified protocol deviations are documented (entered by the monitor in EDC) and classified by category and type (important/not important). In addition, nonoverlapping programmatic checks for protocol deviations are run by both the Sponsor and the EDC vendor. Programmatically identified

protocol deviations are also entered/uploaded to the EDC and classified by category and type (important/not important).

### 5.2.1 Important Deviations

Important protocol deviations are defined by ICH E3 (ICH, 1996) as those “that might significantly affect the completeness, accuracy, and/or reliability of the study data or that might significantly affect a participant’s rights, safety, or well-being”. Examples of important protocol deviations include:

- Participants who were enrolled/randomized but did not meet study eligibility criteria.
- Participants randomized but not treated.
- Participants with misrandomization or stratification errors.
- Participants who received a prohibited prior or concomitant medication or vaccine.
- Participants who previously received an investigational CHIKV vaccine/product, including but not limited to prior vaccination in EBSI-CV-317-004.
- Other deviations from key study procedures such as accidental unblinding or participant noncompliance with assessment of primary outcome measures (e.g., missing serum samples, significantly out of window assessments).

### 5.2.2 Reporting of Protocol Deviations

All protocol deviations are contained in the Study Data Tabulation Model (SDTM) datasets. Protocol deviations assessed as important are tabulated by treatment group and listed by participant for the randomized population (see Section 7.2).

Deviations excluding participants from any analysis population are finalized prior to unblinding. Reasons for exclusion from analysis populations are summarized by treatment group for all randomized participants and listed by participant.

## 5.3 Analysis Populations

Analyses are based on the following study populations:

**Randomized Population:** All screened participants who provide informed consent and provide demographic and other screening measurements and are randomized (i.e., have a randomization number assigned within the EDC system). Most baseline summaries and the IP administration summary use the randomized population.

**Exposed Population:** All participants in the randomized population who receive IP.

**Safety Population:** All participants in the exposed population who provide safety assessment data. This generally includes any participant who was not lost to follow-up at Day 1 (baseline), as they are at risk for reporting an SAE. Participants are analyzed as treated (i.e., according to the treatment a participant received, rather than the treatment to which the participant was randomized). All safety analyses use the safety population.

**Modified Intent-to-Treat (mITT) Population:** All randomized participants who are vaccinated and have at least one post-injection anti-CHIKV human SNA assay result. Participants are counted in the group to which they were randomized. Primary and secondary immunogenicity analyses are repeated for the mITT population as a measure of robustness of the results.

**Immunogenicity Evaluable Population (IEP):** The IEP includes all participants in the mITT population who:

- Provide evaluable serum sample results for the relevant post-vaccination time points, and within the required time frames:
  - Day 22: Day 19 through Day 27, inclusive.
- Have no measurable ( $\geq$ LLOQ) anti-CHIKV human SNA assay titer at Day 1 (baseline), i.e., seronegative at baseline. Note that participants with missing Day 1 (baseline) are excluded from IEP.
- Have no important protocol deviation deemed exclusionary or other reason to be excluded as defined prior to unblinding.

The IEP is the primary population for all immunogenicity analyses.

**CHIKV Genotype Subset:** The CHIKV genotype subset includes those IEP participants who received PXVX0317 and are selected for genotype analysis. See Section 8.4.3 for details.

#### 5.4 Analysis Groups

Tables are displayed by treatment group (PXVX0317 and placebo) columns and overall, for selected tables only.

#### 5.5 Analysis Time Points

For immunogenicity analyses, anti-CHIKV SNA samples are collected at Day 1 (baseline), Day 15 (-1/+3 days), Day 22 (-1/+3 days) and Day 183 EOS (-14/+7 days). For IEP membership, Day 22 has a wider window of Day 19 through Day 27, inclusive. For the time points other than the primary analysis (Day 22), all available data are included in the summaries according to the analysis set defined for a participant's inclusion.

Immunogenicity data are checked and, if another visit or unscheduled sample collection occurred closer to the nominal study day than the scheduled sample collection entered as the nominal visit, the visit data are replaced by the closer visit data when the analysis visit is assigned. In other words, the labeled database visit may not match the derived analysis visit; this procedure is necessary to mitigate the risk of data entered in an incorrect visit in the database. See also Section 5.7 describing handling of multiple sample collections in an analysis window.

Otherwise, unscheduled visit data are not presented in the by-visit summary analyses but are included in the summary tables by maximum toxicity grade or abnormality when applicable, and in data listings by participant.

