6.4 Scheduled Study Visits

Visit 3, Day 15 (-1/+3 days):

- Review diary or memory aid (electronic or paper)
- PI assessment of reactogenicity (Sections 8.1.8, 8.1.9)
- Solicited AEs, unsolicited AEs, MAAEs, SAEs, and AESI evaluation (Sections 3.2.9, 3.2.10, 3.2.11)
- Review concomitant medications
- Targeted physical examination (as needed)
- Blood collection for anti-CHIKV SNA

Visit 4, Day 22 (-1/+3 days)

- Unsolicited AEs, MAAEs, SAEs, and AESI evaluation
- Review concomitant medications
- Targeted physical examination (as needed)
- Blood collection for anti-CHIKV SNA and CHIKV antibodies to neutralize strains representing all CHIKV genotypes

Visit 5, Day 29 (± 1 day) (Telephone Contact)

- Unsolicited AEs, MAAEs, SAEs, and AESI evaluation
- Review concomitant medications

Visit 6, Day 92 (± 3 days) (Telephone Contact)

- MAAEs, SAEs, and AESI evaluation
- Review concomitant medications (only if associated with MAAEs/SAEs/AESI)

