## **5.7 Multiple Records in an Analysis Window**

If more than one sample is collected for anti-CHIKV human SNA assay assessment for a given time point, the sample closest to the nominal time point is used for analysis tabulations. If there is a tie (i.e., the two samples are an equidistant number of days from the nominal time point), then the geometric mean of the two titers is used for analysis tabulations. All samples are reported with database visit and analysis visit in data listings by participant.

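### The closest-sample rule in SAP 5.5 has no day limit, so a correctly labelled Day 18 Visit 3 sample can displace a Day 27 sample that the IEP accepts for Day 22

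*SAP*

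**What the plan says.** SAP 5.5 gives the collection windows as "Day 15 (-1/+3 days), Day 22 (-1/+3 days) and Day 183 EOS (-14/+7 days"), and Protocol 6.4 agrees for Visit 3: "Visit 3, Day 15 (-1/+3 days"). Visit 3 may therefore be drawn on Days 14-18 and Visit 4 on Days 21-25. SAP 5.5 then adds: "For IEP membership, Day 22 has a wider window of Day 19 through Day 27, inclusive". SAP 5.3 makes that range an IEP criterion ("Day 22: Day 19 through Day 27, inclusive").

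The replacement rule follows in SAP 5.5. It applies "if another visit or unscheduled sample collection occurred closer to the nominal study day than the scheduled sample collection entered as the nominal visit", and then "the visit data are replaced by the closer visit data when the analysis visit is assigned". The reason given is that "this procedure is necessary to mitigate the risk of data entered in an incorrect visit in the database".

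SAP 5.7 covers several samples collected for one time point: the closest is used and, if two are equally close, "then the geometric mean of the two titers is used for analysis tabulations".

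SAP 6.5.3 places a participant whose Day 22 result falls before Day 19 or after Day 27 in the modified intent-to-treat (mITT) population but not in the IEP. Its only explicit use of a Day 15 value for Day 22 is a last-observation-carried-forward sensitivity analysis for a missing Day 22 result.

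**The concern.** The rule is wider than its purpose. It is meant to catch samples filed under the wrong visit, but its trigger is distance alone. It has no maximum distance, no link to the Day 19-27 window, no condition that the label be wrong, and no statement that a sample may serve only one analysis visit.

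Day 22 seroresponse and GMT are the coprimary endpoints, and the IEP is their primary population. A rule that can put a correctly labelled Visit 3 titer in the Day 22 position affects either the value analysed or who is analysed. Because the order of the two steps is not stated, two programmers could follow the SAP and build different primary datasets.

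**Working it through.** **Plan's own figure, for context.** SAP 4.1 states power above 99.9% with 180 evaluable per arm and 5% seroresponse on placebo. The vaccine rate is redacted, so it is treated as an assumption and varied. Two-sided alpha is 0.05.

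Power = Φ{[(p1 − p2) − 1.96·√(2p̄(1 − p̄)/n)] / √([p1(1 − p1) + p2(1 − p2)]/n)}

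- p1 = 0.24, p2 = 0.05, n = 180: (0.19 − 1.96 × 0.0371)/0.0357 = 3.28, so power is 99.95%.
- p1 = 0.23: 99.89%. Every rate tried above 0.24, up to 0.90, gives more than 99.9%.
- 180/(1 − 0.10) = 200 per arm, as planned.

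The stated power is reproduced for any vaccine rate of about 0.24 or more. With an assumed rate of 0.50 it stays above 99.9% at 160 per arm.

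**Distances.** For a sample on day d, the distance is |d − 22|.

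| Sample | Days | Distance from Day 22 |
|---|---|---|
| Visit 3 in its window | 14-18 | 8 down to 4 |
| Visit 4 in its window | 21-25 | 0 to 3 |
| Day 22 sample in the IEP window | 19-27 | 0 to 5 |

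**Enumeration.** Replacement needs the Visit 3 sample to be strictly closer than the Visit 4 sample.

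- Both visits in their own windows (5 × 5 = 25 pairs): no replacement and no tie. The nearest Visit 3 is 4 days away and the furthest Visit 4 is 3.
- Visit 3 on Days 14-18, Visit 4 anywhere on Days 19-27 (5 × 9 = 45 pairs): one replacement, Day 18 over Day 27 (4 against 5 days). There are two ties: 18/26 (4 and 4) and 17/27 (5 and 5).
- Visit 3 late, on Day 19 or 20 (3 or 2 days away), with Visit 4 later and up to Day 27: five replacements (19/26, 19/27, 20/25, 20/26, 20/27) and two ties (19/25, 20/24). In 20/25 the displaced sample is inside Visit 4's own window.
- Visit 3 on Days 14-18, Visit 4 on Days 28-31 (20 pairs): 14 replacements and 3 ties. Neither sample is in the IEP window, so these matter for mITT only.

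These are counts of day combinations. They are not patient frequencies, which the documents do not give.

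**What happens to the 18/27 participant**

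- IEP membership judged on any sample from Days 19-27: the Day 27 sample keeps the participant in, and the Day 18 titer is analysed as the coprimary value.
- IEP membership judged on the assigned Day 22 value: Day 18 precedes Day 19, so SAP 5.3 and 6.5.3 take the participant out although the Day 27 sample qualifies.
- mITT: no window applies, so the Day 18 titer stands.

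**Effect of the limit.** If only Days 19-27 may supply the Day 22 value, no sample from Days 14-18 qualifies. Replacements fall from 1 to 0 of 45, and ties from 2 to 0.

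**The case against.** The strongest reply is that closest-to-nominal assignment is ordinary practice, the case is rare, and the replacing sample is by construction nearer the target than the one it displaces. Much of that stands. A Visit 3 sample on Day 19 or 20 is nearer Day 22 (3 or 2 days) than Day 15 (4 or 5 days) and lies inside Days 19-27, so moving it is defensible. What remains there is double use: nothing explicitly stops the same serum also serving as the Day 15 value, and SAP 5.5 keeps all available data at time points other than Day 22. Against this, SAP 5.5 and 5.7 speak of the analysis visit of a sample, which suggests one per sample. The text does not settle it.

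The documents do not support four stronger readings that a reader might infer:

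- **Any in-window Visit 4 sample is exposed.** With both visits inside their protocol windows, none of the 25 pairs is affected. The Day 27 sample is in-window only for the IEP and is two days past Visit 4's own window.
- **SAP 5.7 averages a Visit 3 titer into Day 22.** A tie is not closer, so it does not trigger SAP 5.5. SAP 5.7 covers samples collected for the same time point, and a Visit 3 sample is collected for Day 15.
- **Both harms occur together.** For the 18/27 pair, analysing the early titer in the IEP and removing the participant from it are alternatives.
- **The substituted titer is grossly early.** Replacing samples on Days 18-20 come 4 to 2 days before Day 22, and the samples they displace are 3 to 5 days late.

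**Conclusion.** The point holds in a narrow form. SAP 5.5, as written, lets a correctly labelled Visit 3 sample that is inside its own window replace a Day 22 sample that SAP 5.3 accepts, and it leaves the consequence for the IEP undetermined. This is a stated rule with an unintended result, because its declared purpose is only to correct visits entered wrongly.

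The size is small. With Visit 3 on time, one day combination of 45 is affected, and it needs Visit 3 on its last permitted day and Visit 4 two days late. That few participants would be affected is a judgement from this pattern, since the documents give no distribution of visit days. No threat to power or to a coprimary conclusion is shown. The conclusion rests on reading the replacement rule literally and on the absence of a stated order between visit assignment and the IEP check. Severity: minor.

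**What to change.** In SAP 5.5:

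1. Allow a replacement for Day 22 only by a sample collected on Days 19-27.
2. Do not move a sample that lies in its own visit's window.
3. Assign each sample to one analysis visit only.
4. State that IEP membership and the analysed Day 22 titer are based on the same sample.

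In SAP 5.7, state that the tie rule applies only to samples assigned to the same analysis window.

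The rule's purpose survives: a sample drawn on Day 22 but filed as Visit 3 is outside Days 14-18 and inside Days 19-27, so it can still be moved. Condition 1 alone would not settle the late Visit 3 cases. A Day 20 sample could still replace a Day 25 one, but condition 3 would stop it from also serving as Day 15.

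The cost is a few sentences and a programming condition, set before unblinding. No new data are needed.
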